6.6.1 Handling of Subjects Assigned an Alternating Dose Frequency

Some subjects are assigned an alternating dose frequency. To match any given dose to one of the two alternation options, the actual infusion's dose level (IU/kg) and time passed since last infusion will both be compared to the two alternations assigned. The infusion will then be paired with the alternation option that matches closest to the actual infusion. If such comparison is inconclusive, the planned dose (IU/kg) as recorded in the subject diary will be used to pair the infusion with one of the alternation options.

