
 1. Thrombin generation assay (TGA) parameters (lag time, time to peak thrombin generation, peak thrombin generation, and endogenous thrombin potential [ETP]) 2. Bleed and pain severity scores as measured by the Haemo-SYM questionnaire 3. HRQoL as assessed using EQ-5D and mental domain and component scores of the SF-36 4. Healthcare resource utilization 	
INVESTIGATIONAL PRODUCT(S), DOSE AND MODE OF ADMINISTRATION	
Active Product	
BAX 855 Dosage form: injection, powder, lyophilized, for solution
 
Dose and Dosage frequency: BAX 855 dose will be PK-guided to maintain FVIII target trough levels of 1-3% or approximately 10% (8-12%) at the following dosing frequencies: FVIII trough levels of 1-3%: approximately twice weeklyⁱⁱ FVIII trough levels of approximately 10% (8-12%): every other dayⁱⁱⁱ
 
Mode of Administration: intravenous bolus

SUBJECT SELECTION	
Targeted Accrual	Approximately 116 subjects will be enrolled to have 96 subjects evaluable (48 in each prophylaxis dosing arm).
Number of Groups/ Arms/Cohorts	2

Inclusion Criteria for Subjects Transitioning from Another BAX 855 study:
 
 1. Subject has completed the end of study visit of a BAX 855 study or is transitioning from the ongoing Continuation Study 261302 2. Subject is either receiving on-demand or prophylactic treatment with BAX 855 and had an ABR of ≥ 2 documented and treated during the past 12 months 3. Subject is human immunodeficiency virus negative (HIV-); or HIV+ with stable disease and CD4+ count ≥ 200 cells/mm³, as confirmed by central laboratory 4. Subject is willing and able to comply with the requirements of the protocol 
Inclusion Criteria for Newly Recruited Subjects:
 
 1. Subject is 12 to 65 years old at the time of screening 2. Subject has severe hemophilia A (FVIII clotting activity <1%) as confirmed by central laboratory OR by historically documented FVIII clotting activity performed by a certified clinical laboratory, optionally supported by a FVIII gene mutation consistent with severe hemophilia A 3. Subject has been previously treated with plasma-derived FVIII concentrates or recombinant FVIII for ≥ 150 documented EDs 	

ⁱⁱ Twice weekly: infusion on day 3 or 4, at 2 different doses to cover the different treatment intervals, or every 3.5 days. According to individual PK, frequency may be adjusted based on FVIII trough levels.

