8.7.5 BAX 855 Prophylaxis Dosing

FVIII trough level of 1-3%:

BAX 855 will be administered twice weekly, with either:

- Infusion with alternating 3- and 4-day infusion intervals; the doses will be different if a 3- or a 4-day interval needs to be covered
- An infusion every 3.5 days
- Depending on subject's individual PK, different dosing intervals should be considered, in particular if single doses of 80 IU/kg are required or regular FVIII peak levels of 200% would be reached or exceeded

^{vi} In case a subject underwent a PK determination in any of the BAX 855 studies, the PK assessment may have to be repeated based on the sponsor's evaluation.

FVIII trough level of approximately 10% (8%-12%):

- BAX 855 will be infused every other day.
- Depending on subject's individual PK, a different dosing interval may be considered to prevent regular high FVIII peak levels

The required dose and frequency will be provided by the sponsor. Subjects must adhere as closely as possible to the dosing regimen. If a dose is missed, it must be documented and the next dose will be taken as soon as possible. After this dose, the regularly scheduled regimen will be resumed. Subjects requiring treatment for a breakthrough bleeding episode should resume their PK-tailored prophylaxis as soon as the bleeding episode is resolved.

The days of the week on which treatment is administered may be selected by the subject and/or his/her physician and should provide maximum coverage for vigorous activities. To provide some flexibility, the weekly schedule in terms of the days of the week may be changed during the course of the study to best accommodate potential changes in the subject's life style. However, the initially calculated and adjusted, if applicable, dose regimen should be maintained.

For each subject, the BAX 855 infusions to perform PK(s), IRs and the first individualized prophylaxis dose of BAX 855 at the Baseline visit, which includes an IR assessment, must be administered in the hospital/clinic setting under medical supervision. All other treatments may be self-administered, administered by a parent or caregiver, or administered in the clinic or hospital setting. Each subject's physician will determine the setting of treatment administration. If the subject will self-administer BAX 855, the investigator will ensure that the subject and/or his caregiver have been adequately trained.

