where TL_{target} is the target trough level (1.7% or 10%) and $TL_{predicted,\tau}$ is the TL predicted for an infusion interval of τ under the current dose for this interval. The latter will be calculated as:

$$TL_{predicted,\tau} = 0.5 * \left(\frac{Dose_{current,\tau}}{Dose_1} * TL_{measured,t1} * 2^{\frac{t1-\tau}{HL}} \right) + \frac{Dose_{current,\tau}}{Dose_2} * TL_{measured,t2} * 2^{\frac{t2-\tau}{HL}}$$

^{vii} This additional visit may coincide with regular scheduled study visit.

where $Dose_1$ and $Dose_2$ are the actual doses (in IU/kg) of the infusions after which the trough levels $TL_{measured,t1}$ and $TL_{measured,t2}$ were measured, $t1$ and $t2$ are the times in hours post start of infusion for each trough level collection, τ is the infusion intervals for which the prediction is being made, and HL is the terminal half-life of the initial PK assessment.

In case the FVIII levels are below the required lower limit, the BAX 855 dosage may be increased up to a maximum of 80 ± 5 IU/kg and/or the dosing frequency may be increased. Doses as high as 80 IU/kg may be used, provided the FVIII peak level does not exceed 200%. Otherwise, the frequency of prophylactic infusions has to be increased.

In subjects with severe hemophilic arthropathy and/or target joints^{viii} who continue to experience recurrent bleeding episodes, an imaging technology such as magnetic resonance imaging (MRI) or ultrasound of the affected joint(s) has to be applied to verify the presence of a bleed.

Also, if at any time during the course of the study, a subject starts to experience an unexpected high bleeding rate or experiences bleeding episodes that do not adequately respond to BAX 855 therapy, he/she will be evaluated for the presence of inhibitory and total binding antibodies to FVIII, BAX 855 and PEG, and clinically managed at the discretion of the investigator. It is also recommended to perform an IR determination.

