4.4 Per-Protocol Analysis Set (PPAS)

The Per Protocol Analysis Set (PPAS) is to comprise all subjects in the FAS who:

- Completed the second 6 months (ObsDay 183 to ObsDay 364) of prophylactic treatment. Defined as not having prematurely discontinued from the study.
- Had no major deviations from the protocol affecting the study results.

Major protocol deviations are defined in the Protocol Deviation Plan. Protocol deviations are obtained from the following sources:

- IQVIA Clinical Trial Management System (CTMS).
- Programmatic testing by IQVIA Biostatistics.
- The end of study, final Data review/analysis set assignment meeting.

During the course of the study, data review meetings (for data cleaning) will be held on a regular basis. During these meetings the quality of the data will be assessed.

Prior to performing any final analysis as set out in this Statistical Analysis Plan (SAP), a meeting will be held discussing the impact of any major protocol deviation on the analysis. If a subject presents with a major protocol deviation, it is not in itself cause to exclude the subject from the PPAS. Only at the protocol deviation discussion meeting will the decisions be made on whether a subject should be excluded from the PPAS or not, taking the major protocol deviation information into consideration. The meeting should be attended by participants from at least Biostatistics and Medical.

Below is a list of possible major deviations that may influence the study results, which will be discussed at the protocol deviation discussion meeting:

- Subjects less than 75% exposed to BAX 855 as derived in Section 6.6: Measurements of Treatment Compliance.
- Subjects less than 75% compliant to planned dosing regimen as discussed in Section 6.6: Measurements of Treatment Compliance.
- Use of expired or temperature compromised IP.
- Use of a Pegylated product other than BAX 855.

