6.6 Measurements of Treatment Compliance

A subject listing (using the SAS) and summary tables (using the SAS, PPAS and PKAS) on compliance.

Treatment compliance will be derived using results and derivations obtained from study exposure as described in Section 6.5: Extent of Exposure.

Treatment compliance will be based on the following:

- Adherence to the study medication administration schedule; and
- Adherence to recommended prophylactic dosing plan.

An infusion will be considered in adherence to the study medication administration schedule if it does not deviate by more than ± 8 hours from the PK-guided assigned dosing frequency:

Based on the treatment regimen, time that a subject was not covered by BAX 855 prophylaxis, will be determined. The time in minutes that a subject was not covered by BAX 855 prophylaxis is calculated as the sum of all time periods exceeding the planned infusion interval after a prophylactic infusion.

Time not exposed (minutes) should be set to 0 if the above derivation results in number of days less than 0.

The percentage of time a subject was covered by BAX 855 prophylaxis, should be derived as follows:

$$\begin{aligned} & \textit{Time Covered by Prophylaxis (\%)} \\ &= \frac{\textit{OPE(Minutes)} - \textit{Total Time not Covered (Minutes)}}{\textit{OPE(Minutes)}} \times 100 \end{aligned}$$

An infusion is considered to be in adherence to the recommended prophylactic dose if the actual amount infused (IU/kg) is between 90% and 110% of the planned/assigned dose (IU/kg) to be infused. Infusions with actual amount infused not recorded in the eCRF, will be excluded from the compliance calculations.

The number and percentage of infusions in adherence to the recommended prophylactic dosing plan, will be determined for each subject using the overall number of infusions for that subject as denominator.

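### SAP 6.6.1 matches alternating-regimen infusions on the interval before the dose, although the protocol sizes each dose for the interval after it, so compliance can be mis-scored

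*SAP*

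**What the plan says.** Protocol 8.7.5 allows twice-weekly dosing in the 1-3% arm with alternating 3- and 4-day intervals, where "the doses will be different if a 3- or a 4-day interval needs to be covered". The synopsis footnote describes infusions "at 2 different doses to cover the different treatment intervals", and the adjustment formula in Protocol 8.7.6 predicts the trough at the end of an interval "under the current dose for this interval". All three tie a dose to the interval that comes after it.

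SAP 6.6.1 assigns each infusion of an alternating subject to one of two options. The infusion's "dose level (IU/kg) and time passed since last infusion will both be compared to the two alternations assigned", and the closest option is taken. There is a fallback: "If such comparison is inconclusive, the planned dose (IU/kg) as recorded in the subject diary will be used". The SAP does not say what an option contains or how closeness is measured.

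SAP 6.6 then applies three measures.
- Schedule: an infusion may deviate by at most 8 "hours from the PK-guided assigned dosing frequency".
- Dose: "An infusion is considered to be in adherence to the recommended prophylactic dose if the actual amount infused (IU/kg) is between 90% and 110" per cent of the assigned dose.
- Time covered: loses any time beyond the planned interval after each prophylactic infusion.

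SAP 4.4 lists, for discussion at the deviation meeting, "Subjects less than 75% compliant to planned dosing regimen as discussed in Section" 6.6, and separately subjects less than 75% exposed.

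**The concern.** Time since the last infusion is the interval that the previous dose had to cover. Take a Monday/Thursday schedule. Monday's 3-day dose comes 96 h after Thursday's, and Thursday's 4-day dose comes 72 h after Monday's. A subject who does exactly what was assigned therefore presents the 3-day dose with a 4-day elapsed time, and the reverse, at every infusion. A subject who takes the two doses in the wrong order presents a consistent pair every time. The matching rule favours the wrong pattern.

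At stake is whether the compliance tables describe these subjects correctly, and whether the right ones come up when per-protocol membership is discussed. Bleeding-rate comparisons are repeated in the per-protocol set (SAP 7.1.2).

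**Working it through.** The documents give no figure for this point, so there is none to reproduce.

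**Inputs.** Intervals of 72 h and 96 h (Protocol 8.7.5); tolerances of ±8 h and 90-110% (SAP 6.6); 16 h half-life (SAP 9.2), with 12 to 20 h as an assumed range; target trough 1.7% (Protocol 8.7.6). Mono-exponential decay without carry-over is assumed, which is also how the 8.7.6 formula scales.

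**Gap between the options.** Time: 96 − 72 = 24 h, three times the 8 h tolerance. Dose for the same trough: D4/D3 = 2^(24/HL).
- HL 12 h: 2^2 = 4.00
- HL 16 h: 2^1.5 = 2.83
- HL 20 h: 2^1.2 = 2.30

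Paired with the wrong option at 16 h, a dose reads as 283% or 35% of plan. The doses would fall within the 90-110% window of each other only at a half-life of about 24/log2(1/0.9) = 158 h to 24/log2(1.1) = 175 h or more.

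**Scores.** A strict 72/96 h alternation was run for a perfect complier and for a swapper. Reading A compares time since the last infusion with the interval paired to that same infusion. Reading B compares it with the interval paired to the previous infusion. Entries are dose % / schedule % / time covered %.

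| Reading of ±8 h | Pairing decided by | Complier | Swapper |
|---|---|---|---|
| A | dose or diary | 100 / 0 / 100 | 100 / 100 / 85.7 |
| A | elapsed time | 0 / 100 / 85.7 | 100 / 100 / 85.7 |
| B | dose or diary | 100 / 100 / 100 | 100 / 0 / 85.7 |
| B | elapsed time | 0 / 0 / 85.7 | 100 / 0 / 85.7 |

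The 85.7% is (168 − 24)/168: one 24 h excess per week. Diary pairing assumes that the diary's planned dose is the one actually assigned and infused.

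**Undefined closeness.** Adding absolute differences in hours and IU/kg makes the result depend on dose size. With doses of 10.6 and 30 IU/kg, a complier's 3-day dose at 96 h lies 24 units from its own option and 30 − 10.6 = 19.4 from the other, so time wins. With 21.2 and 60 IU/kg the distances are 24 and 38.8, so dose wins. Summing relative differences gave dose pairing in all four dose sets tried.

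**What the swapper's doses would do.** With a 1.7% target and a 16 h half-life, the 3-day dose stretched over 96 h gives 1.7/2.83 = 0.6%, and the 4-day dose over 72 h gives 1.7 × 2.83 = 4.8%. Both are outside 1-3%.

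**The case against.** The strongest reply is that 6.6.1 only assigns a dose to an option and does not define the schedule check. The one direction that 6.6 fixes is forward, in the time-covered measure. If the ±8 h check follows that convention, and conflicting criteria count as inconclusive so that the diary decides, the complier scores 100% throughout and the swapper fails on schedule. This stands: a reader might infer that compliers always score 0% somewhere and swappers always pass, but the documents do not fix the reading on which that depends. What remains is that the correct result is reached only when dose or diary overrides the elapsed-time criterion. Where elapsed time decides, the complier scores 0% on dose under either reading.

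It is also fair that the swapper is not clean on every measure. Time covered is 85.7%, although that is above 75% and raises no exposure flag. Troughs are measured at most site visits, so persistent swapping could show up elsewhere.

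On per-protocol membership, a reader might infer that compliers would be excluded. SAP 4.4 says that a major deviation does not by itself exclude anyone; a meeting decides. Time covered is 85.7% or 100% in every scenario, so the exposure item is never triggered. For the compliance item, SAP 6.6 defines a per-subject percentage of infusions only for dose adherence, so whether a schedule failure alone reaches the 75% threshold is unstated.

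A reader might also infer a proven one-sided distortion between arms. SAP 6.6.1 refers to some subjects without naming an arm, Protocol 8.7.5 permits other intervals in both arms and a fixed 3.5-day schedule in the 1-3% arm, and no count is given.

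**Conclusion.** The point holds in limited form. The direction of the elapsed-time criterion in SAP 6.6.1 contradicts the protocol's dose sizing. That follows from the text alone: in a correct 3/4-day alternation dose and elapsed time disagree at every infusion, and they agree when the doses are swapped.

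The effect on scores is conditional. With the ±8 h check tied to the same infusion's option, a perfect complier loses all of one adherence measure and a swapper passes both. With the previous infusion's interval and dose or diary pairing, both are scored correctly. The 2.8-fold dose gap rests on the 16 h half-life and mono-exponential decay, but no plausible half-life brings the two doses within 10% of each other.

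The reach is the compliance tables (safety, per-protocol and PK sets) and the under-75% compliance item for the per-protocol discussion. It probably falls mainly on the 1-3% arm, because the 3/4-day alternation is described there; the number of subjects is unknown. Nothing supports an effect on the primary analysis: SAP 7.1.2 uses recorded bleeds regardless of compliance with planned infusions. The correction should be made because the rule as written is wrong and the change is cheap.

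**What to change.** In SAP 6.6.1, define each alternation option as a dose plus the interval that follows it. Pair each prophylactic infusion by its dose and the time to the next prophylactic infusion, keep the diary's planned dose for inconclusive cases, and state how closeness is measured when hours and IU/kg disagree.

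In SAP 6.6, state that the ±8 h check and time covered are both judged against the interval assigned to the infusion that opens it.

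With pairing by dose, this gives the complier 100 / 100 / 100 (dose / schedule / covered) and the swapper 100 / 0 / 85.7. If a swapper's conflict were settled by time instead, dose adherence would fail (35% and 283% of plan at 16 h), so the swap is visible either way.

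The cost is a few sentences in the SAP and a lead in place of a lag in the compliance program. No new data are needed, and dosing in the trial does not change.

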7. EFFICACY EVALUATION

7.1 Analysis of Primary Efficacy Outcome Measure

The primary efficacy measure is the proportion of subjects with an ABR = 0 per treatment arm during the second 6-month period of the study (ObsDay 183 to ObsDay 364). Other measurements of bleeds are part of the secondary and exploratory outcome measurements as documented in Section 7.2: Analysis of Secondary Efficacy Outcome Measure and Section 11: Exploratory Analyses.

7.1.1 Hypothesis Regarding Primary Efficacy Outcome Measure

The null hypotheses of no difference between the two treatment arms will be tested against a two-sided alternative.

H₀: Proportion Low Level subjects with ABR of 0

=

Proportion High Level subjects with ABR of 0

versus

H_a: Proportion Low Level subjects with ABR of 0

≠

Proportion High Level subjects with ABR of 0

7.1.2 Bleeding Episodes

Subject listings will be presented for the following items using the analysis set indicated in brackets:

- Bleeding episodes treated with BAX 855 including efficacy ratings (FAS).
- Bleeding episodes not treated with BAX 855 (FAS).
- Annualized bleeding rate and interval between bleeding episodes (SAS).
- Course of target joints (SAS).
- Magnetic resonance imaging and ultrasound (SAS).

Summary tables will be presented for the following items using the analysis set indicated in brackets:

- Descriptive statistics on annualized bleeding rate (FAS, PPAS) presented by age group, geographical location and race,.
- Comparisons presented by age group and race on:
 - Annualized bleeding rate overall and for the second 6-month study period (FAS and PPAS).
 - Sensitivity Analysis on ABR during the second 6-month study period (FAS).
- Comparisons presented by age group and race on observed annualized bleeding rate (FAS and PPAS).
- Comparisons presented by age group on:
 - Average coagulation parameters against ABR using the Spearman rank correlation coefficient, both overall and for the second 6-month study period (FAS and PPAS).
 - Reduction on ABR (FAS and PPAS).
 - Descriptive statistics on average interval between episodes [Months] (FAS and PPAS).
 - Bleeding episodes (FAS).
 - Hemostatic efficacy against number of BAX 855 infusions to treat perioperative bleeds (FAS).
- Presented by age group, bleed type, bleed severity, bleed location and bleed timing:
- Characteristics of bleeding episodes treated with BAX 855 (FAS).
- Hemostatic efficacy against number of BAX 855 infusions to treat bleeds (FAS).

Figures will be presented for the following items using the FAS:

- Dot and whisker plot (point and 95% CI) of ABR (by treatment arm).
- Multi bar plot of subject treatment profile with infusions, bleeding episodes and antibody titers.
- Linear regression plot of average observed factor VIII trough levels (IU/dL) against observed ABR.
- Linear regression plot of TGA against observed ABR.

The following information items are obtained from the eCRF:

- Bleeding episodes (Bleeding Episode eCRF panels).
- Target joints (Haemophilia A History/Blood Group/Target Joint Identification and Development of new Target Joints eCRF panels).
- Infusions to treat bleeding episodes and prophylactic infusions prior to bleeds (Study Infusion eCRF panels).
- Ultrasound (Ultrasound eCRF panel).

The following derivations will be made based of the eCRF reported results:

- The following anatomical bleeding sites are considered to be joints:
 - Left wrist.
 - Right wrist.
 - Left elbow.
 - Right elbow.
 - Left shoulder.
 - Right shoulder.
 - Left hip.
 - Right hip.
 - Left knee.
 - Right knee.
 - Left ankle.
 - Right ankle.
- An identified joint will be considered a target joint if:
 - The joint is identified as a target joint from either the Haemophilia A History/Blood Group/Target Joint Identification or the Development of new Target Joints eCRF panel.

- There were at least four spontaneous bleeding episodes within a consecutive 6-month period in the joint.
- A joint will cease to be considered a target joint if identified in the eCRF with less than four spontaneous bleeds within a consecutive 6-month period in the joint.
- A bleeding site will be considered a target joint if the specific joint is considered a target joint at the time of the bleed.
- A bleeding site will be considered a non-target joint if the specific bleed is not considered a target joint at the time of the bleed. The bleeding site will still be considered as a joint.
- A bleed will be considered an injury related bleed if the cause is indicated as “Injury”.
- A bleed will be considered a spontaneous bleed if the cause of the bleed is identified as “Spontaneous” or “Unknown” in the eCRF.
- A bleed will be considered a major bleed if the severity is indicated as “Major”.
- A bleed will be considered a moderate bleed if the severity is indicated as “Moderate”.
- A bleed will be considered a minor bleed if the severity is indicated as “Minor”.
- A bleed will be considered a weekday bleed if the bleed occurred on a Monday, Tuesday, Wednesday, Thursday or Friday.
- A bleed will be considered a weekend bleed if the bleed occurred on a Saturday or Sunday.
- A bleed will be considered a morning bleed if the bleed occurred between 04:00 and 11:59.
- A bleed will be considered an afternoon bleed if the bleed occurred between 12:00 to 17:59.
- A bleed will be considered a night bleed if the bleed occurred between 18:00 and 03:59.
- A bleed is considered to have occurred at an unknown time if the time of a bleed is not available.
- Time since last prophylactic infusion in hours should be derived as:

$$\text{Time (h)} = (\text{Date/Time of Bleed} - \text{Start Date/Time of Infusion}) / (60 \times 60)$$

